## PROTOCOL SYNOPSIS

TITLE	Concurrent use of Lymphoseek and Indocyanine Green for sentinel lymph node detection in endometrial cancer – a prospective study
STUDY PHASE	Feasibility
INDICATION	Sentinel lymph node sampling in clinically uterine confined early-stage endometrial cancer
INVESTIGATIONAL PRODUCT OR PROCEDURE	Concurrent use of Lymphoseek and Indocyanine Green in minimally invasive surgery
PRIMARY OBJECTIVE(S)	To determine the detection rate of bilateral sentinel lymph nodes with the concurrent use of Lymphoseek and Indocyanine Green as compared to each agent alone.
SECONDARY OBJECTIVE(S)	
(1) To determine the overall detection rate of sentinel lymph nodes with concurrent use of Lymphoseek and Indocyanine Green
 
(2) To determine location and number of Lymphoseek-positive sentinel lymph nodes preoperatively by single-photon emission computed tomography (SPECT/CT imaging) and intraoperatively by a laparoscopic handheld gamma detection
 
(3) To determine the location and number of Indocyanine Green-positive sentinel lymph nodes by intraoperative infrared fluorescent imaging
 
(4) To determine the concordance of Lymphoseek-positive sentinel lymph nodes with intraoperatively detected Indocyanine Green-positive sentinel lymph nodes, and vice versa, the concordance of Indocyanine Green-positive sentinel lymph nodes with Lymphoseek-positive sentinel lymph nodes.
 
(5) To assess the safety of the concurrent use of Lymphoseek and Indocyanine Green

TREATMENT SUMMARY	
Sentinel lymph node assessment
 
 
- Preoperatively, within 24 hours prior to surgery, the subject will receive in the nuclear medicine suite of Stanford Hospital injections of 0.125 mCi or 0.5 mCi each Lymphoseek into the uterine cervix at 3, 6, 9, and 12 o'clock. Immediate and delayed static planar images will be obtained with and without a transmission source. SPECT-CT of the abdomen and pelvis will be obtained for further characterization.
 
- Subjects will then undergo minimally invasive endometrial cancer surgery. The SPECT/ CT images will be available for review to the surgeon prior to the start of the surgery.
 
- In the operating room, following anesthesia induction, the uterine cervix will be injected with 0.5 mL each of Indocyanine Green at positions of 3, 6, 9, and 12 o'clock.
 
- The surgery will start with the identification and dissection of
 

	sentinel lymph nodes using near infrared imaging and the gamma probe.
SAMPLE SIZE	30 patients over 1 year
STATISTICAL CONSIDERATIONS	
The analysis population will include all patients who complete the study procedures specified above. We do not expect missing data or loss-to-follow up since the outcome is ascertained at the time of surgery. Patients who do not adhere to the study treatment plan of both injections, SPECT/CT and surgery with sentinel lymph node assessment will not be included in the analysis population.
 
To address our primary objective, we plan to enroll 30 patients with concurrent use of lymphoseek and indocyanine green over 1 year. The primary analysis is the calculation of the bilateral SLN detection rate which will be calculated as the number of patients with bilateral SLN detection divided by the total number of patients.
 
With 30 participants and assuming a true bilateral detection rate of 80%, the probability of correctly concluding that our approach has an acceptable bilateral detection rate (i.e., 24 patients being detected with bilateral SLNs) is 61%. The probability of incorrectly concluding this (assuming that the true detection rate is 69%) is low at 13%. We will deem the approach used in this study promising if we observe a bilateral detection rate of at least 80%.

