## 1. OBJECTIVES

### 1.1 Primary Objective

To determine the detection rate of bilateral sentinel lymph nodes with the concurrent use of Lymphoseek and Indocyanine Green.

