### 9.2 Secondary Outcome

(1) Overall detection (yes/no): For each subject, an assessment will be made of whether there was overall sentinel node detection. A sentinel lymph node will be defined as being detected if it is detected on the pre-operative SPECT/CT imaging scan or intraoperatively using near-infrared imaging or the handheld gamma detection device. If at least one SLN is detected (on any side), then this outcome will be considered a ‘Yes’.

(2) Location and number of SLNs detected by Lymphoseek: The location and number of sentinel lymph nodes detected by Lymphoseek will be assessed. A sentinel lymph node will be defined as being detected by Lymphoseek if it is detected using the pre-operative SPECT/CT imaging scan and/or intraoperatively using the gamma detection device.

(3) Location and number of SLNs detected by Indocyanine Green: The location and number of sentinel lymph nodes detected by Indocyanine Green will be assessed. A sentinel lymph node will be defined as being detected by Indocyanine Green if it is detected intraoperatively using near-infrared imaging only and not by the gamma detection device.

(4) Adverse events and severe adverse events will be monitored and reported.

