### **11.4.2. Analysis Plan**

The analysis for this study is primarily descriptive as the primary objective is to determine the detection rate of bilateral SLNs. The bilateral SLN detection rate will be calculated as the number of patients with bilateral SLN detection divided by the total number of patients. If the bilateral detection rate is at least 80%, we will deem this approach promising in detecting bilateral SLNs.

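### The synopsis primary objective compares the combination with each agent alone, but no analysis does so; and section 9.2(3), read literally, drops near-infrared nodes that the gamma device also finds

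*Combined protocol and SAP*

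**What the plan says.** **Primary objective and analysis**

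- The synopsis gives the primary objective as "To determine the detection rate of bilateral sentinel lymph nodes with the concurrent use of Lymphoseek and Indocyanine Green as compared to each agent alone".
- Section 1.1 stops earlier: "To determine the detection rate of bilateral sentinel lymph nodes with the concurrent use of Lymphoseek and Indocyanine Green".
- The synopsis statistics paragraph says: "The primary analysis is the calculation of the bilateral SLN detection rate". Section 11.4.2 adds the decision rule: "If the bilateral detection rate is at least 80%, we will deem this approach promising in detecting bilateral SLNs".
- Section 2.4 describes a single-group design. Section 9.1 counts a sentinel node found by SPECT/CT, near-infrared imaging or the gamma device, and requires at least one on each side.
- The reference rate in 11.6.2 and 11.6.3 is 69%, which section 2.1 reports as the centre's own bilateral rate with Indocyanine Green (ICG). Section 2.2 says that nothing has been published on Lymphoseek in endometrial cancer.

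**Which nodes belong to which agent**

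- Section 9.2(2) counts a node as Lymphoseek-detected "if it is detected using the pre-operative SPECT/CT imaging scan and/or intraoperatively using the gamma detection device".
- Section 9.2(3) counts a node as ICG-detected "if it is detected intraoperatively using near-infrared imaging only and not by the gamma detection device".
- Synopsis secondary objective (3) has no such exclusion: "To determine the location and number of Indocyanine Green-positive sentinel lymph nodes by intraoperative infrared fluorescent imaging". Objective (4) asks for concordance in both directions, including "the concordance of Indocyanine Green-positive sentinel lymph nodes with Lymphoseek-positive sentinel lymph nodes". Section 1.2(3) asks for the same.
- Section 4 plans that nodes seen on near-infrared are then confirmed with the gamma counter.
- Section 11.5.2 counts the patients with nodes found by each agent and applies McNemar's test, on the 11.5.1 population.

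**The concern.** There are two gaps, and both concern what each agent contributes.

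**A. An objective without an analysis.** A reader of the synopsis expects a bilateral rate for ICG, one for Lymphoseek, and a statement of how much the combination adds to each. None is planned. The 80% rule describes the level of detection with everything combined. The McNemar test in 11.5.2 does not fill the gap: it is secondary, it is not about bilateral detection, and it sets one agent against the other rather than the combination against either.

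**B. A definition that works against its own objective.** Under 9.2(3) as worded, a near-infrared node that the gamma device confirms, which is the course section 4 plans, leaves the ICG count. Section 9.2(2) has no matching exclusion, so the distortion runs one way: the ICG count falls and the Lymphoseek count does not. At stake are the ICG node count, the concordance result, the McNemar test, and any ICG-alone rate that the synopsis objective would need.

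**Working it through.** **1. The plan's own figures.** Inputs from 11.6.2: n = 30, threshold 24, true rates 69% and 80%. With X binomial:

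- P(X ≥ 24 | 30, 0.80) = 0.607 (plan: 61%).
- P(X ≥ 24 | 30, 0.69) = 0.133 (plan: 13%).
- Exact 95% interval for 24/30: 61.4% to 92.3% (plan: 61% to 92%).

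All three reproduce. They describe one combined rate against fixed values. No single-agent rate from the trial's own patients enters.

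**2. What could stand for each agent alone.**

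| Comparator | In the plan |
|---|---|
| ICG alone | 69%, historical, same centre; no bilateral rate planned from trial patients |
| Lymphoseek alone | no benchmark; no bilateral rate planned from trial patients |

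**3. What 9.2(3) does to a node, read literally.**

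| Near-infrared | Gamma device | SPECT/CT | ICG, 9.2(3) | Lymphoseek, 9.2(2) |
|---|---|---|---|---|
| yes | yes | either | no | yes |
| yes | no | yes | yes | yes |
| yes | no | no | yes | no |

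Only the first row is distorted.

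**4. From nodes to patients.** Section 11.5.2 counts patients, so one node found by both methods changes nothing if the patient keeps another qualifying near-infrared node. A patient becomes falsely Lymphoseek-positive and ICG-negative only when the probe finds every one of her near-infrared nodes.

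Assumptions, for illustration:

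- Both agents map the same nodes, and every mapped patient is Lymphoseek-positive (by SPECT/CT if not by the probe), so true discordance is 0.
- 26 of 30 patients are mapped, from the 88% overall ICG rate in section 2.1 (0.88 × 30 = 26.4, taken as 26).
- 0.69 × 30 = 20.7 are mapped on both sides and 26 − 20.7 = 5.3 on one side.
- There are k nodes per mapped side, and the probe finds each independently with probability c. Neither value is in the documents.

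Expected falsely discordant patients = 20.7 × c^(2k) + 5.3 × c^k.

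| c | k = 1 | k = 2 |
|---|---|---|
| 0.5 | 5.18 + 2.65 = 7.8 | 1.29 + 1.33 = 2.6 |
| 0.8 | 13.25 + 4.24 = 17.5 | 8.48 + 3.39 = 11.9 |
| 0.9 | 16.77 + 4.77 = 21.5 | 13.58 + 4.29 = 17.9 |

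With all discordance in one direction, the exact two-sided McNemar p-value is 2 × 0.5^n. For 3 against 0 it is 0.25. For 12 against 0 it is 0.0005. For 18 against 0 it is 0.000008. The effect therefore runs from no significant result to a strong false signal.

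**5. Precision of a descriptive comparison.** If the combination gained 3 of 30 patients over one agent, the gain would be 10%, with exact 95% interval 2.1% to 26.5%.

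**The case against.** **A looks like a slip in one synopsis clause.** Section 1.1, the synopsis statistics, 11.1, 11.4.2 and 11.6.2 all describe one proportion in a feasibility study. This stands, and it is why deleting the clause is an acceptable repair.

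**The section 2.3 hypothesis is not wholly unmeasured.** A reader might infer that nothing in the plan bears on whether Lymphoseek improves detection. The documents do not support that: setting 80% against the 69% of current practice is a comparison, though indirect, historical, and limited to ICG.

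**9.2(3) may only name ICG's device.** Beside 9.2(2), it can be read as saying that near-infrared imaging, not the gamma device, defines ICG detection. That may well be the intention, and the figures in the working apply only to the literal reading. But the text does not say so, and two readings can give two results from the same data.

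**Stronger readings of 9.2(3) do not hold.** A reader might infer that overlap between the agents is forced to zero, or that every node found by both becomes a discordant observation. Neither follows. A node seen on near-infrared and SPECT/CT but missed by the probe counts for both agents, and the test counts patients.

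**Neither intraoperative rate is truly an agent alone.** The surgeon has the SPECT/CT images, and the probe is used to confirm near-infrared nodes. This stands. It limits what a retained comparison can show and has to be stated with it.

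**Conclusion.** Both points hold on the text. The synopsis sets a comparison that section 1.1 omits and no analysis addresses. Section 9.2(3), read literally, conflicts with synopsis objectives (3) and (4), with 1.2(3), and with the workflow in section 4.

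The size of A is not a number: the comparison with Lymphoseek alone has no reference at all, and that with ICG alone has only a historical one. The size of B is 2.6 to 21.5 falsely discordant patients of 30. That range rests on the literal reading, on assumed probe sensitivity of 50% to 90%, on independence between nodes, and on one or two nodes per side.

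A reader might conclude that the primary result is compromised. It is not. Section 9.1 pools all three methods and does not use the 9.2(3) exclusion, so the endpoint, the 24-of-30 rule and its 13% and 61% stand. The wording should be corrected before analysis, but the design need not change.

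**What to change.** 1. **Section 9.2(3).** State that a node seen on near-infrared imaging counts as ICG-detected whether or not the gamma device also finds it. Align 1.2(2), which lists near-infrared imaging among the means of finding Lymphoseek-positive nodes. This is needed whichever option is taken in item 2.
2. **Synopsis and section 1.1.** Make them agree. Either delete the comparison with each agent, or keep it as descriptive. If kept, report in 11.4.2 the bilateral rate by ICG, by Lymphoseek and by the combination (as defined in 9.1), and the within-patient gain over each agent, all with exact 95% intervals. Give no p-value for the gain, because the combination cannot fall below either component in the same patients.
3. **Section 11.5.2.** Run the between-agent analysis on patients who received both agents; the 11.5.1 population can include women removed before ICG. Report agreement in both directions: of Lymphoseek-positive nodes, the share ICG-positive, and the reverse. McNemar's test compares marginal rates and does not measure concordance.
4. **Limits to state.** SPECT/CT guidance and gamma confirmation mean that neither intraoperative rate is an agent alone. Detections on SPECT/CT only, which 9.1 counts, may inflate the gain over ICG. Thirty patients support estimation only.

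**Cost.** A text modification approved under section 10.1, and possibly one per-side case report form field. The forms are not in the documents, but the study calendar already lists near-infrared and gamma detection as separate items. No extra patients, injections or imaging are needed. If the comparison is kept, its price is wide intervals.

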**SCHEMA**

## LIST OF ABBREVIATIONS AND DEFINITION OF TERMS

ADL	Activities of daily living
AE	Adverse event
BSA	Body surface area
CBC	Complete blood count
CD	Cluster of differentiation
CI	Confidence interval
CRF	Case report/Record form
CTCAE	Common Terminology Criteria for Adverse Events
DSMC	Data Safety Monitoring Committee
ECG	Electrocardiogram
EMCA	Endometrial cancer
FDA	Food and Drug Administration
FIGO	International Federation of Gynecology and Obstetrics
GCP	Good Clinical Practice
GI	Gastrointestinal
Hgb	Hemoglobin
IC-GREEN	Indocyanine Green
IRB	Institutional Review Board
IV	Intravenous
OP	Operative
OR	Operation room
PANES	Preoperative anesthesia
PD	Protocol Director
PLT	Platelet
SAE	Serious adverse event
SLN	Sentinel lymph node
SPECT/CT	Single-photon emission computed tomography
SRC	Scientific Review Committee
Tc 99m	Technetium 99m
WBC	White blood cell
WHO	World Health Organization

## 1. OBJECTIVES

### 1.1 Primary Objective

To determine the detection rate of bilateral sentinel lymph nodes with the concurrent use of Lymphoseek and Indocyanine Green.

### 1.2 Secondary Objectives

- (1) To determine the overall detection rate of sentinel lymph nodes with concurrent use of Lymphoseek and Indocyanine Green;
- (2) To determine the location and number of Lymphoseek-positive sentinel lymph nodes preoperatively by single-photon emission computed tomography (SPECT/CT imaging) and intraoperatively by a laparoscopic handheld gamma detection device and near-infra-red fluorescent imaging;
- (3) To determine the concordance of Lymphoseek-positive sentinel lymph nodes detected by SPECT/CT and/or gamma probe with intraoperatively detected Indocyanine Green-positive sentinel lymph nodes, as well as reverse concordance.
- (4) To assess the safety of the concurrent use of Lymphoseek and Indocyanine Green.

## 2. BACKGROUND

### 2.1 Study Disease

Endometrial cancer accounts for 50% of all gynecological malignancies in the US. The majority are diagnosed at an early stage. Although clinically locally confined, endometrial cancers may have microscopically spread to lymph nodes; therefore, International Federation of Gynecology and Obstetrics (FIGO) revised the endometrial cancer staging in 1988 to make it a surgical staging system and included a complete pelvic lymphadenectomy [1]. Despite the increased accuracy in staging, complete lymphadenectomy has not been shown in randomized trials to increase progression-free or overall survival [2, 3]. Instead, complete lymphadenectomy carries the risk of increased morbidity, including lymph edema and nerve damage. To reduce this morbidity while maintaining prognostic information, the concept of sentinel lymph node (SLN) sampling has been introduced [4, 5].

Various tracers have been used to identify the first draining lymph node, the sentinel lymph node, and assess for tumor involvement. In the thus-far largest multicenter prospective trial, detection rates for SLNs in minimally invasive surgery for endometrial cancer using Indocyanine Green alone have been reported as only 52% bilaterally and 86% overall [6]. Our own institutional data shows detection rates using Indocyanine Green of 69% and 88%, bilaterally and overall, respectively [7]. If a sentinel lymph node is detected, surgery is restricted to the removal of the SLN and a complete lymphadenectomy is avoided. If no lymph nodes are mapped, current guidelines recommend a complete lymphadenectomy on the side where no sentinel lymph node was detected. Thus, for 30-50% of patients the morbidity of a complete lymphadenectomy cannot be avoided.

### 2.1.1 Tracers for sentinel lymph node detection

Historically, sentinel lymph node sampling was first described in the late 70's for penile cancer using the injection of radiocolloids [8]. Subsequently, sentinel lymph node sampling has become standard of care in cutaneous melanoma and breast cancer [9, 10]. Vulva cancer was the first gynecologic malignancy where sentinel lymph node sampling was tested [11, 12]. The role of sentinel lymph node mapping in endometrial carcinoma is under evaluation [13].

In endometrial cancer, as in all other cancer entities, radioactive tracers, or dyes, either non-fluorescent or fluorescent, or combinations of radioactive tracers and dyes have been employed. The radioactive tracers used are filtered or non-filtered sulfur colloids, most commonly radiolabeled with technetium-99m (Tc 99m). The major advantage of radioactive tracers is deep tissue penetration and the ability to detect sentinel lymph node locations preoperatively. Reported overall detection rates are 92-96% with a bilateral detection rate of 73-80% [14, 15]. Concerns regarding the use of radioactive colloids are (i) the unspecific and passive distribution of the tracer colloids throughout the lymphatic system by lymph flow and/or diffusion which diminishes the retention of the tracer in the first draining lymph node and results in the leakage of radiotracers to subsequent lymph nodes and thereby the detection of the second or third lymph node stations instead of the actual sentinel lymph node; (ii) the need for preoperative injection and imaging; and (iii) the handling of radioactivity.

To simplify the intraoperative detection and avoid the use of laparoscopic gamma counters, various dyes have become available, i.e. Isosulfan Blue 1%, Methylene Blue 1%, Patent Blue 2.5% sodium. Isosulfan Blue is the only dye that has been FDA-approved for sentinel lymph node detection. Overall and bilateral detection rates have been reported at 63-78% and 40-46%, respectively [16-18]. Disadvantages of Isosulfan Blue are (i) the costs, (ii) a significant risk of an anaphylactic reaction (1.1%) and (iii) the comparably poor deep tissue penetration, especially of fat tissue. There is evidence from breast cancer on the equivalence of Methylene Blue and Isosulfan Blue [19] and reported overall and bilateral detection rate for Methylene Blue in robotic-assisted laparoscopic surgery in endometrial cancer are 86% and 52% [20]. Methylene Blue is less expensive, and has a lower, but still significant risk of allergic reactions. Furthermore, combinations of blue dyes and radioactive tracer colloids have been used in endometrial cancer, with reported overall and bilateral detection rates of 90-97% and 65-76%, respectively [21-23].

Recently, Indocyanine Green has emerged as useful imaging dye that requires a near-infrared camera for localization. One main advantage of a near-infrared fluorescent dye over a blue dye is the improved visibility through visceral fat. Overall and bilateral detection rates have been reported as 86-96% and 52-88%, respectively [6, 16, 18, 24, 25]. Compared to blue dyes, allergic reactions are very rare. Indocyanine Green is now commonly used in many practices [13]. However, the thus-far largest prospective multi-center study, the FIRES study, reports an overall detection rate of 86% and a 52% bilateral detection rate only. Higher detection rates have mainly been reported by single-center studies. Disadvantages of Indocyanine green are (i) the required special equipment, i.e. near-infrared camera, and (ii) the problem of leakage which is inherent to all unspecific radioactive and colored tracers and thereby the diminished retention in the first draining lymph nodes and the possibility of detecting lymph nodes subsequent in the lymph node chain.

## 2.2 Study agent - Lymphoseek

(99m)Tc-diethylenetriaminepentaacetic acid (DTPA)--mannosyl-dextran (Lymphoseek) was first synthesized and described in 2001 by Vera et al. [26]. In contrast to all other dyes and tracers used in sentinel lymph node detection, this synthetic radiotracer was specifically designed for sentinel lymph node mapping. The molecule has a molecular weight of 35.8 kDa and a diameter of 7.1 nm and consists of a dextran backbone and 8 DTPA groups. The DTPA groups are used for the chelation of Tc 99m Technetium.

55 mannose residues are covalently bound to the dextran backbone. These 55 mannose residues provide high receptor affinity to the mannose receptor CD 206 which is highly enriched on the surface of macrophages and dendritic cells. Lymphoseek has a dissociation constant of 0.12 nmol/L. This low dissociation constant ensures the effective uptake of the agent by the lymph node and improved retention and thus a lower distal lymph node accumulation than seen for the nonreceptor-targeted filtered Tc 99m-sulfur colloid [27]. Accordingly, Lymphoseek accumulates in fewer lymph nodes with higher specificity [28].

Furthermore, the dextran backbone guarantees rapid injection site clearance which entails the rapid diffusion from the injection site through lymph and blood vessels. In fact, neutral dextrans show an interstitial diffusion coefficient 10-fold greater than for proteins of the same hydrodynamic radius, a property which has been attributed to hydrophilicity and flexibility of the dextrans and the absence of charge. A radiotracer that clears more rapidly from the injection site, even if the tracer delivers equal activity to the sentinel node, will provide higher signal-to-noise ratio by reducing the unspecific background and thus better a detection rate than an agent with slower clearance [27].

While Lymphoseek has been FDA-approved in breast cancer, melanoma, and head and neck cancer [29], no published studies exist for the use of Lymphoseek in endometrial cancer.

